We will recruit individuals from the Boston area who meet the inclusion and exclusion criteria listed in **Table 5**. Recruitment will take place through several venues. First, we will recruit from those who have already completed our MODERATE randomized trial (N>200 who have completed so far). The vast majority these individuals still reside in Boston. MODERATE participants have provided consent to be re-contacted for future studies. We will use the MODERATE database to identify individuals who may be eligible for our study, and contact them directly to invite them to participate.

Second, we will simultaneously attempt to enroll study participants who fulfill the age and BMI requirements using routine media outlets in the local community and also online advertising. These include: (1) billboards placed in Boston mass-transit buses and subways; (2) advertisements in local print media, such as the Boston Metro and the Boston Globe; (3) online advertisement with websites such as Craig's List and Oodle (these sites have been productive sources for recruitment in the past).

Third, we will use recruitment opportunities provided through Partners, such as Partners RSVP, and ClinicalTrials@Partners.

We will include both men and women and all races and ethnicities. The only exception will be women who are pregnant because certain medications used during the inpatient evaluations (e.g., nitroglycerine), and certain study medications (i.e., captopril) are contraindicated during pregnancy.

Table 5. Eligibility Criteria

Inclusion Criteria

- BMI ≥ 30 kg/m²
- Age ≥ 18 years
- HbA1c 5.7-6.4%
- Self reported sleep <7 hours per night

Exclusion Criteria

- Current or prior history of diabetes mellitus
- Use of hypoglycemic meds or random serum glucose ≥ 200 mg/dL
- Estimated GFR <60 mL/min/1.73m²
- Inability to extend sleep by 1 hour per night
- Pregnant or breast-feeding
- Preexisting lung disease requiring oxygen

- Preexisting CVD
- Active or uncontrolled psychotic disorder
- Active or uncontrolled bipolar illness
- Active malignancy within the prior 5 years
- Use of antihypertensive meds
- Hepatic impairment
- Job requires rotating night shifts
- Bariatric surgery within the prior 12 months
- Use of hypnotic meds
- Hematocrit <36%(women) or <41% (men)
- Use of natural sleep aids
- Known allergy/intolerance of ACE inhibitors
- History of stroke
- Recent (within 2 weeks of study) or upcoming travel across time zones

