- Known obstructive sleep apnea or use of continuous positive airway pressure
- Insomnia
- Known allergy to melatonin
- Hypertension Type 1 or 2 (BP >150/90)
- Lactose Intolerance
- Autoimmune Disease

[figure not shown]
Subject Enrollment

Responders to advertisements will be pre-screened by telephone to obtain a BMI estimate and a medical history to gauge potential eligibility (**Table 5**). For those who may be eligible following this phone query, the basic study schema (**Figure 1**) will be described to identify those who remain interested in participation after learning the duration, inpatient requirements, and potential medication use. These individuals will then be invited to attend an outpatient screening visit.

We anticipate that the sex and race/ethnicity breakdown of subjects enrolled into EMC-PILOT will be similar to that which we have experienced in the MODERATE trial. Thus far in the MODERATE trial, enrolled subjects are 63% female, 28% black, 7% more than one race, and 13% Hispanic.

The pilot study is a double-blind, placebo-controlled randomized trial, in which 16 subjects with obesity (BMI \geq 30 kg/m²), pre-diabetes (HbA1C, 5.7-6.4%), and self-reported short sleep duration (<7 hours/night) are randomly assigned 1:1 to receive either placebo or 2 mg of controlled-release melatonin, taken orally every evening 1 hour before bed for 6 weeks. **All subjects will be asked to extend their sleep time by one hour** during the 6 week period between inpatient visits. Endpoints will be measured at both the baseline and 6-week inpatient visits.

Figure 1: Schema for pilot study with sleep extension and nightly melatonin as treatments.

Screening Visit: Screening visits will take place at the Brigham and Women’s Outpatient Center for Clinical Investigation (CCI; [name]). During the outpatient screen, [name] will explain the study in detail, review the consent form, and answer questions. After obtaining written informed consent for participation, a history and physical examination will be performed in order initially judge eligibility based upon the criteria set out in **Table 5**. Those individuals deemed potentially eligible based upon the screening history and exam will undergo phlebotomy and analysis for HbA1c, serum chemistries and glucose, and CBC to confirm eligibility using the criteria presented in the table.

[figure not shown]
Study Procedures

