Pre-admission: All participants will wear a wrist activity monitor for a total of 8 weeks; 2 weeks prior to the baseline inpatient visit and for the 6 weeks between inpatient visits, **Figure 2**. They will complete a daily sleep log during the 2 weeks preceding the baseline visit and 6 weeks preceding second visit. Three days before admission, participants will be placed on a high salt diet by supplementing their usual diet with 150 mmol sodium/day for 3 days using dry bouillon added to food. All participants will also be asked to do a 24 hour diet recall for the day before admission.

Treatment assignments: Prior to admission for the baseline visit, **subjects will be randomized (1:1)** to receive study medication (melatonin 2mg of controlled release formulation or placebo). **All subjects will be asked to extend their sleep time by one hour** during the 6 week period between inpatient visits.

Baseline and Follow-up inpatient visit: Baseline and 6-week inpatient visits will be virtually identical. Each inpatient visit will begin at 4:00PM on Day 0 and end at 4:00PM on Day 1, **Figure 2**.

Figure 2: Schema for inpatient visit studies at 6-week visit.

Day 0 — We will complete two 12-hour urine collections for each subject. All subjects will begin the first 12-hour urine collection at their home at 7:00AM on day 0 of admission to the Brigham and Women’s Hospital Center for Clinical Investigation (CCI). The first 12-hour urine collection will be ended at 7:00PM that evening. The second 12-hour collection will begin and continued overnight until 7:00AM on day 1. The nurses will keep the daytime (7AM to 7PM) and nighttime (7PM to 7AM) urine separate to permit analysis of diurnal variation in urinary analytes. Subjects will fast after 9 pm to ensure a 12-hour fast by the next morning.

[figure not shown]

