Central Blood Pressure — Will be measured using pulse wave analysis using the SphygmoCor system (AtCor Medical, West Ryde, NSW, Australia), which measures central blood pressure and arterial stiffness.

Glucose metabolism — Will be evaluated by applying the Oral Minimal Model method to the results of a 2 hour 7- measurement, mixed meal tolerance test.² Subject will be given breakfast in the form of a mixed meal (10kcal/kg, 45% carbohydrate, 15% protein, 40% fat, 1g/kg glucose) which must be consumed within 15 minutes with glucose, insulin and c-peptide measured from arterialized blood drawn at 0, 10, 20, 30, 60, 90 and 120 minutes from start of meal. Glucose will be measured using a YSI glucose analyzer (CV <2%) for rapid measurement (YSI, Inc, Yellow Springs, OH), insulin will be measured with a radioimmunoassay (CV=10%) and c-peptide will be measured using an electrochemiluminescence

immunoassay(CV=12%). From the glucose, insulin and c-peptide measurements calculation of insulin sensitivity (reciprocal of insulin resistance) and β -cell responsiveness will be calculated.

Drugs to be used:

Captopril - The 25mg oral dose of captopril used during the renal specific RAAS measurement. Severe hypotensive reactions to a single dose of captopril are very uncommon in our experience among those we've studied who were free from pre-existing HTN, particularly in high sodium balance; nevertheless, participants will undergo constant monitoring during the RPF study, and the study will be stopped if the BP following captopril falls below 90 mmHg systolic or 50 mmHg diastolic, at which point the participant will receive medical treatment from the attending physician. Captopril may also be associated with angioedema, but typically occurs after repeated doses and even so the risk is <1%.

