Potential complications to participants include: (i) the discomfort from having phlebotomy; (ii) the discomfort from having intravenous peripheral catheters placed during CCI admissions; (iii) potential side effects from being on a high salt diet for 3 days, such as elevation of BP or hypokalemia; (iv) potential side effects from medications administered during the inpatient CCI stays, including drop in BP from oral captopril consumption (for the renal plasma flow study (RPF)); (v) side effects from melatonin such as allergic reaction, medication interactions, and elevation of liver function tests; and finally (vi) the chance

of a confidentiality breach such that personal information becomes de-identified and linked to the results of the various studies and blood tests.

- i. Phlebotomy: This risk will occur by study design but is minimal.
- ii. Peripheral intravenous catheter placement: This risk will occur by study design but is minimal.
- iii. High salt diet: A high salt diet is common to the US population, and enrolled participants will not have pre-existing HTN or hypokalemia; thus, a high salt diet for 3 days is unlikely to cause harm.
- iv. Inpatient procedures: Severe hypotensive reactions to the oral captopril are very uncommon in our experience among those we've studied who were free from pre-existing HTN; nevertheless, participants will undergo constant monitoring during the RPF study, and captopril will not be given if the BP prior to scheduled captopril administration is less than 100 mmHg systolic or 60 mmHg diastolic.
- v. Side effects from Melatonin: The tolerability of controlled-release melatonin has been widely studied. In the largest series, 791 subjects were evaluated for 3 weeks in a randomized placebo-controlled trial; adverse event rates were 0.8% with melatonin and 0.6% with placebo. After 3 weeks, 711 subjects were re-randomized for an additional 26 weeks; during this prolonged period, the incidence of adverse events was 0.6% and 0.7% in melatonin and placebo arms, respectively. In a separate, smaller open label study of controlled-release melatonin, the most common adverse events attributed to melatonin were dizziness and headache. Controlled-release melatonin was found to have no effect on psychomotor function or memory in adults relative to placebo.

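### The salt-load safety rationale assumes that nobody enrolled has hypokalemia, but Table 5 has no potassium criterion, and its hypertension entry is not reconciled with the same rationale

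*Combined protocol and SAP*

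**What the plan says.** Under Study Procedures (Pre-admission), every participant is salt-loaded by "supplementing their usual diet with 150 mmol sodium/day for 3 days" ahead of admission.

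The opening list of Risks and Discomforts includes "potential side effects from being on a high salt diet for 3 days, such as elevation of BP or hypokalemia". Item iii of that section then answers this risk. It first observes that salt-heavy diets are widespread in the United States, and continues: "enrolled participants will not have pre-existing HTN or hypokalemia; thus, a high salt diet for 3 days is unlikely to cause harm".

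The eligibility rules are in Table 5 (Subject Selection). Two of its exclusions bear on blood pressure: "Use of antihypertensive meds" and "Hypertension Type 1 or 2 (BP >150/90", where the bracket closes after the figure. No inclusion or exclusion criterion mentions potassium.

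The Screening Visit text says that blood is taken for "analysis for HbA1c, serum chemistries and glucose, and CBC to confirm eligibility using the criteria presented in the table".

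**The concern.** Item iii argues from a premise to a conclusion: the load is unlikely to do harm because the people receiving it will be free of two conditions. Those conditions correspond to the two example harms that the same section attributes to the load. A premise of this kind is only as good as the eligibility rule that enforces it. If no rule does, someone outside the stated safety assumption can be enrolled in full compliance with the protocol and given the load.

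The load is also taken before admission, added to the participant's usual diet, so the close supervision described for the inpatient procedures does not cover it. What is at stake is whether the written risk assessment matches the population that the protocol admits. The validity of the trial's estimates is not in question.

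**Working it through.** No arithmetic applies. The check sets each part of the premise in item iii beside the rule that would have to deliver it.

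**1. No hypokalemia**

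- *Table 5.* It lists 4 inclusion and 26 exclusion criteria. The laboratory quantities with a numeric limit are HbA1c, random serum glucose, estimated GFR and hematocrit. Potassium is absent, so the number of potassium criteria is 0.
- *Screening Visit.* The chemistries are tied to the criteria in the table ("analysis for HbA1c, serum chemistries and glucose, and CBC to confirm eligibility using the criteria presented in the table"). As the table has no potassium criterion, a low value breaches no stated rule.
- *Inpatient measurements.* Serum potassium is not among the measurements set out under Parameters Measured.
- *Protections Against Risk.* This section promises to exclude people more likely to be harmed by the study medications, and mentions laboratory screening for biochemical effects. The salt load is a dietary preparation using bouillon, and no analyte or limit is named.
- *Monitoring and quality assurance.* An investigator committee looks weekly at out-of-range safety results and can end an individual's participation. This is discretionary and does not define who may enroll.

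Result: the premise is asserted, and no written eligibility rule enforces it.

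**2. No pre-existing hypertension**

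- *Table 5.* There are 2 relevant criteria: use of antihypertensive drugs, and "Hypertension Type 1 or 2 (BP >150/90".
- *Reading A.* The bracket is the plan's definition of hypertension. No other threshold for it appears in the documents, so on this reading the premise is met.
- *Reading B.* The named diagnosis excludes by itself and the bracket only illustrates it. The premise is again met.
- *Reading C.* The bracket is the operative test at screening, while item iii means any earlier diagnosis. A person once diagnosed, now untreated and at or below 150/90, would then pass Table 5 and fall outside the premise. Some support for this reading comes from the way Table 5 refers explicitly to the past for diabetes and stroke but not for hypertension.
- The entry also leaves open whether one or both of the two pressures must exceed the limit.

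Result: the match depends on which reading is intended, and the documents do not say.

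**3. Exposure**

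All participants take the load before the baseline visit. The six-week visit is described as nearly the same as the baseline visit, so a second load is likely but is not separately stated. The sample size is given as 20 in Specific Aims and Potential Benefits, and as 16 in Subject Enrollment and Biostatistical analysis. The documents give no frequency of low potassium or of earlier hypertension in this population, so the number affected cannot be estimated.

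**The case against.** The strongest reply is that the plan has adequate practical protection. Chemistries are drawn at screening, participants are expected to be otherwise healthy, a committee reviews safety results weekly, and a clinician who saw a low potassium might well act on it. Item iii also does not rest on the two absences alone, since it appeals first to how common such diets are. All of this is fair, and it weakens any suggestion that an abnormal value would be ignored. It does not supply the rule that item iii presupposes.

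On hypertension the reply is stronger still. The plan excludes treated people and gives a numeric limit, and Subject Selection describes the target population as pre-hypertensive. On its own terms the premise may be fully met.

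Four stronger readings are tempting, and the documents do not support them:

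- *Hypertensive people can enroll, contrary to item iii.* A reader might infer this from the 150/90 figure. Calling people at or below that figure hypertensive on their readings needs a definition from outside the documents. Only the ambiguity stands.
- *Neither condition is properly excluded.* This depends on the same outside definition. Hypokalemia has no criterion; hypertension has two, one of them unclear.
- *The captopril rationale also assumes normal potassium.* It does not mention potassium. Drugs to be used refers to people "who were free from pre-existing HTN, particularly in high sodium balance", and item iv says "Severe hypotensive reactions to the oral captopril are very uncommon in our experience among those we've studied who were free from pre-existing HTN". Both report past experience and make no claim about who will be enrolled. They are accompanied by constant monitoring and by blood-pressure limits before and after the dose.
- *Participants were given a wrong risk assessment.* The consent form is not among the documents, so this cannot be checked.

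**Conclusion.** The point holds in a narrow form. The no-hypokalemia premise in item iii has no matching entry in Table 5, and the chemistries drawn at screening are tied to a table that does not use potassium. This follows from the protocol's own text. The hypertension part is an unresolved ambiguity about what the bracketed value means and whether an earlier diagnosis excludes.

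Severity is low. No endpoint, analysis or sample-size figure is affected, the trial is a small pilot, and the number of participants concerned is unknown and could be zero. The conclusion assumes that Table 5 is the complete list of eligibility rules, which is how the Screening Visit text treats it.

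**What to change.** Reconcile Table 5 with item iii of Risks and Discomforts in one of two ways:

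- give Table 5 an entry that makes the no-hypokalemia statement true, judged on the screening chemistries already drawn; or
- rewrite the salt-load rationale so that it claims no more than Table 5 delivers.

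In the same amendment, state whether the bracketed pressure defines the hypertension exclusion, whether one or both pressures must exceed it, and whether an earlier diagnosis excludes, so that the entry can be matched to the wording in item iii. Screening blood pressure is already recorded under Data Collection.

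Which clinical rule applies, and any limit, is for the investigators and the IRB. The cost is a short wording amendment. It needs no new blood draw and no change to the analysis; a new eligibility entry could exclude a few candidates at screening.
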